**LIST OF ABBREVIATIONS**

AE	adverse event
ALA	alpha lipoic acid
BUN	blood urea nitrogen
CBC	complete blood count
CFR	Code of Federal Regulations
CRF	case report form
CT	computed tomography
DSMB	Data Safety Monitoring Board
EDC	electronic data capture
FDA	Food and Drug Administration
GCP	Good Clinical Practice
HIPAA	Health Insurance Portability and Accountability Act of 1996
ICF	informed consent form
ICH	International Conference on Harmonisation
IEC	independent ethics committee
IRB	institutional review board kidney
KUB	ureter bladder radiograph
MG	milligrams
PI	principal investigator
QoL	quality of life
SAE	serious adverse experience

## PROTOCOL SYNOPSIS

TITLE	The effect of lipoic acid natural supplement on cystine stone formation
SPONSOR	[name]
FUNDING ORGANIZATION	FDA
NUMBER OF SITES	1 site
RATIONALE	
Cystinuria is an inherited autosomal recessive disorder of the kidney that is the result of an inability to reabsorb cystine from the urine. Supersaturation of cystine in the urine produces crystals that precipitate and form stones in the kidney, which can be a cause of obstruction, infection, and chronic kidney disease. Cystine stones constitute a major health challenge for affected individuals with cystinuria because of the frequent recurrence of painful symptoms and the current absence of effective, patient-accepting treatment.
 
The naturally occurring oral supplement alpha lipoic acid (ALA) has been shown in a mouse model of cystinuria to dramatically slow the initiation of cystine stone formation as well as the growth of existing stones. To date, there have been no published studies on the effect of ALA in individuals with cystinuria.

STUDY DESIGN	This study will be a single center, randomized double-blind placebo-controlled trial designed to assess how daily 1200 mg ALA supplementation for three years affects kidney stone recurrence, quantitative urinary cystine, and stone, blood and urinary metabolomic and metallomic profiles.
PRIMARY OBJECTIVE	Determine the effect of ALA on kidney stone recurrence in participants with cystinuria.
SECONDARY OBJECTIVES	Determine the effect of ALA on quantitative urinary cystine, and metallomic and metabolomics profiles in participants with cystinuria.
NUMBER OF PARTICIPANTS	50
PARTICIPANT SELECTION CRITERIA	
Inclusion criteria: males and females age 18 or older; documented cystinuria on prior 24-hour urine collection and/or stone analysis; history of previous cystine kidney stones; and being able and willing to provide consent.
 
Exclusion criteria: poorly controlled diabetes mellitus (hemoglobin A1C > 8.0% for more than 1 year); current ALA administration at the time of screening; ALA administration within the last year prior to screening; vulnerable populations including incarceration status; anticipation of

	pregnancy during the study duration; unable to give informed consent; non-English primary language; pregnancy, lactation, or child- bearing age without birth control devices; and serious illness likely to cause death within the next 5 years.
TEST PRODUCT, DOSE, AND ROUTE OF ADMINISTRATION	The test product is 600 mg of ALA administered orally twice a day for three years.
CONTROL PRODUCT, DOSE AND ROUTE OF ADMINISTRATION	The control product is a sucrose tablet containing 10 mg of sucrose, given orally twice a day for three years.
DURATION OF PARTICIPATION AND DURATION OF STUDY	Screening: 1 week to determine eligibility Treatment: 3 years with visits every 4 months Follow-up: 2 years with visits every 4 months

CONCOMITANT MEDICATIONS	
Allowed: The participants will be allowed to continue any medications they are currently taking.
 
Prohibited: No medications will be strictly prohibited. However, alpha-mercaptobutyrylthiolglycine and D-penicillamine, two medications currently used to treat cystinuria, are both thought to bind the sulfhydryl groups of cysteine preventing the molecules from binding together and resulting in the insoluble cystine molecule. Both medications are not used with great frequency and both are not very effective. As they may interfere with the mechanism of action of ALA, participants of this study who take alpha-mercaptobutyrylthiolglycine and/or D-penicillamine will be asked to stop these medications 12 weeks prior to starting the treatment portion of the study as a washout period to ensure no harmful effects result from stopping these therapies. If they chose not to stop, at the discretion of the Principal Investigator, the participant will be allowed to participate and the study will simply document the use of Thiola throughout the course of the study and may look at these participants separately in the final analysis.

EFFICACY EVALUATIONS	Efficacy evaluations will include determination of stone recurrences on clinical history, exam, and radiographic review; quantitative 24-hour urinary cystine; and urinary, blood, and stone metallomic and metabolomic profiling.
PRIMARY ENDPOINT	
The primary efficacy endpoint will be assessed in two ways over the course of the 3-year treatment period:
 
 
1) symptomatic stone recurrences, defined as renal colic, stone passage, or surgical removal of a stone;
 
2) silent stone recurrences, classified as stone growth or new stones,
 

	diagnosed on the basis of renal ultrasound, plain KUB x-ray, or if clinically indicated, computed tomography.
SAFETY EVALUATIONS	After participants are enrolled at 3-4 weeks during the treatment period, a study coordinator will contact each participant to check compliance, tolerability, and side effects with ALA supplementation. Any concern for a potential adverse event will be reviewed by the study investigators. Patient clinical care will continue as per the current standard for the duration of this study. Tolerability and side effects will be reviewed at each scheduled clinic visit which normally occur every four months. All reported adverse events will be reviewed by the study investigators. Depending on the severity of the adverse event, the study investigator may determine the need for un-blinding, and the participant may be advised to stop ALA intake if it is determined that ALA is the cause.
PLANNED INTERIM ANALYSES	When 50% of target participants have been enrolled and on the study protocol for 6 months, an interim analysis will be performed by an un-blinded statistician to evaluate for ALA clinical effects.
STATISTICS Primary Analysis Plan	The analysis will be performed on the intention-to-treat principle in the treatment and placebo groups. The primary efficacy endpoint will be assessed by comparing the rates of symptomatic and silent stone recurrences using the t-test with a two-sided p-values and calculated 95% confidence intervals. In addition, the analysis of secondary endpoints will compare quantitative urinary cystine, and metallomic and metabolomics profiles using repeated measures of analysis of variance.
Rationale for Number of Participants	The target enrollment for this study is 50 participants, based on a conservative approach to determine the sample size needed to evaluate the effect of ALA supplementation. Two recent studies evaluating the medical management of cystinuric individuals have reported that among individuals who are compliant in taking medications, the average number of stone events per person is approximately 1 per year (Reference #'s 5, 9). The current study design will be powered at 90% to detect a clinically meaningful reduction of stone events at 50% (0.5 stone events per year) with two-tailed $\alpha = 0.05$ . Based on a two-sided t-test, the following scenarios were considered for the standard deviation (SD) for the sample and sample size (n): SD 0.5, n=11; SD 0.75, n=24; SD 1, n=42. To account for a small dropout rate over the study duration, the enrollment goal of 50 participants was proposed.

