Clinical data including medical history, plain KUB x-ray and renal ultrasound, routine blood work, and 24-hour urine collections for all participants will be collected as part of normal clinical care at routine clinical visit intervals, which currently occur every 4 months. Routine clinical care for participants will not be altered in any way outside of administration of the supplement or placebo. Routine clinical care generally consists of office visits every 4 months at which time, as medically necessary as determined by the study investigator, an imaging study is performed (plain KUB x-ray, ultrasound, or CT scan if clinically indicated), a 24-hour urine collection is done to check quantitative urinary cystine levels, and blood is drawn to evaluate electrolyte levels as well as renal function. During routine visits for blood and urine tests, any discarded blood and urine specimens will be collected for research testing. No additional blood draw or urine collection will be performed for this study. From discarded routine specimens provided during these clinic visits, metallomic and metabolomics profiling will be performed for all participants using discarded samples material. This is comprised of mass spectrometry and elemental analysis of samples performed in our research lab. Quality of life measurement, as recorded by the Wisconsin Stone-quality of life questionnaire (Wisconsin Stone-QoL), will also be evaluated.

Recurrent stone events, defined by symptomatic or silent stone recurrence, is the primary endpoint in this study. It will be documented in this study cohort, and compared between treatment and placebo groups to determine treatment effect. If stones are removed for surgery or spontaneously passed by participants, any discarded stone specimens not needed for clinical care will also be subjected to metabolomic and metallomic analysis.

At the end of the three years of study drug treatment, all participants will undergo a low dose non-contrast CT scan to look for a silent change in stone size. As this is a pilot study, recruitment will be limited to target enrollment of 50 participants (25 for each treatment arm). Treatment will continue for a total of 3 years and after treatment completion, participants will be followed for an additional 2 years to evaluate for change in clinical status or adverse events resultant from ALA administration.

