### 10.1 Visit 1 (Initial Visit)

1. Review the study with the participant (participant's legal representative) and obtain written informed consent and HIPAA authorization.
2. Assign the participant a unique study ID number.

3. Record demographics data.
4. Record medical history, including a history of stone disease and family history of stone disease, date of first diagnosis, and prior surgical interventions.
5. Record concomitant medications.
6. Perform a complete physical examination and record vital signs if possible
7. Administer the Wisconsin Stone-QoL survey.
8. Collect routine blood for clinical laboratory tests (CBCs, chemistries, BUN, creatinine) if medically necessary as determined by the study investigator
9. Perform routine 24hr urine testing.
10. Collect passed stone specimens, if presented.
11. Collect discarded blood and urine specimens for research purposes if presented.

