### 15.3 Sample Size and Randomization

The target enrollment for this study is 50 participants, based on a conservative approach to determine the sample size needed to evaluate the effect of ALA supplementation. Two recent studies evaluating the medical management of cystinuric individuals have reported that among individuals who are compliant in taking medications, the average number of stone events per person is approximately 1 per year (Reference #'s 5, 9). The current study design will be powered at 90% to detect a clinically meaningful reduction of stone events at 50% (0.5 stone events per year) with two-tailed  $\alpha = 0.05$ . Based on a two-sided t- test, the following scenarios were considered for the standard deviation (SD) for the sample and sample size (n): SD 0.5, n=11; SD 0.75, n=24; SD 1, n=42. To account for a small dropout rate over the study duration, the enrollment of 50 participants was proposed. At UCSF, clinical volume approximates 60 nephrolithiasis patients per week, including those with cystinuria. At a recent cystinuria outreach event led by [name] at UCSF (<http://[name].ucsf.edu/?q=news/june-18-2015-cystine-patient-symposium>), over 50 individuals with cystinuria attended among over 100 participants overall. We anticipate that 6-8 months will be required to accrue these participants.

Participants will be computer sequence-randomized to receive either ALA or placebo.

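### The primary t-test on an undefined recurrence rate ignores follow-up time and baseline stone history, and so loses power in a 50-patient trial

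*Combined protocol and SAP*

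**What the plan says.** The synopsis (Primary Analysis Plan) gives the only named test: "The primary efficacy endpoint will be assessed by comparing the rates of symptomatic and silent stone recurrences using the t-test", two-sided, with 95% confidence intervals, by intention to treat. Section 15.2 restates the endpoint and the intention-to-treat principle but names no test, offset, weighting, covariate or rule for partial follow-up.

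The synopsis and section 15.3 size the trial with a two-sided t-test. The control assumption is that "the average number of stone events per person is approximately 1 per year", and the trial is "powered at 90% to detect a clinically meaningful reduction of stone events at 50% (0.5 stone events per year". The scenarios are "SD 0.5, n=11; SD 0.75, n=24; SD 1, n=42". Section 4.1 sets a "target enrollment of 50 participants (25 for each treatment arm".

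Unequal follow-up is foreseen. The enrolment goal was set "To account for a small dropout rate over the study duration", with no figure given. Section 12.4 rules out replacing withdrawals. Section 12.1 asks that people who stop treatment be encouraged to finish the remaining visits, which does not ensure it.

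The Visit 1 list (section 10.1) includes: "Record medical history, including a history of stone disease and family history of stone disease, date of first diagnosis, and prior surgical interventions". No stated analysis or stratification uses this. Section 15 says that a detailed SAP, which may modify the plan, will follow before the final analysis.

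**The concern.** Stone events are recurrent counts, about three per control patient over three years on the plan's own rate. Dividing each count by that person's follow-up and running a t-test treats a noisy short-term rate as being as informative as a three-year one. The intention-to-treat analysis keeps the people with short follow-up, so they add noise out of proportion to the information they carry. Differences between patients in underlying stone activity also stay in the error term, although stone history is taken at entry. At 50 patients there is little power to spare.

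**Working it through.** **1. The plan's own figures.** With z(0.975) + z(0.90) = 1.960 + 1.282 = 3.242 and a difference of 0.5 per year, (SD × 3.242 / 0.5)² gives 10.5, 23.6 and 42.0 for SD 0.5, 0.75 and 1. These match the stated 11, 24 and 42, but this is the one-sample form. A two-arm comparison needs twice as many per arm: 22, 48 and 85. With 25 per arm, two-sample power is Φ(0.5 / (SD × √(2/25)) − 1.960):
- SD 0.5: Φ(3.536 − 1.960) = 94%
- SD 0.75: Φ(2.357 − 1.960) = 65%
- SD 1: Φ(1.768 − 1.960) = 42%

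The sample-size arithmetic is a separate matter. Here it shows how much room the t-test has.

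**2. Cost of equal weighting.** For true rate λ, follow-up T and between-patient (gamma) variance k, a person's observed rate has variance λ/T + kλ². Averaged over arms with λ = 1 and 0.5:
- k = 0 (Poisson only): three years (0.333 + 0.167)/2 = 0.25, SD 0.5; two months (6 + 3)/2 = 4.5, SD 2.1; ratio 18.
- k = 0.5: three years (0.833 + 0.292)/2 = 0.5625, SD 0.75; two months (6.5 + 3.125)/2 = 4.81, SD 2.19; ratio 4.81/0.5625 = 8.6.

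So SD 0.5, the only scenario with at least 90% power at 25 per arm, corresponds to no between-patient variation at all. Two months is an illustration, not a figure from the plan.

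**3. Power by simulation.** From the plan: 25 per arm, 1 versus 0.5 events per year, three years, two-sided 5%. Assumed: k = 0.25, 0.5 and 1.0; exponential dropout; a three-year pre-enrolment count sharing the patient's underlying rate. At 6% per year, about 16% leave over three years, which equals the plan's gap from 42 to 50 (8/50). At 15% per year, about 36% leave. Power at k = 0.25 / 0.5 / 1.0:

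| Dropout | t-test on rates | Overdispersed Poisson, offset | Offset and baseline |
|---|---|---|---|
| 6%/year (800 trials) | 71/56/42% | 78/64/46% | 82/78/74% |
| 15%/year (1,500 trials) | 57/50/35% | 72/61/45% | 76/72/71% |

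Offset gain at 6% per year: 78 − 71 = 7, 64 − 56 = 8, 46 − 42 = 4. At 15% per year: 15, 11 and 10; a repeat gave 13, 13 and 8, so about 9–15 within simulation error. With no dropout the gain is about 0–2 points.

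Further gain from baseline at 6% per year: 82 − 78 = 4, 78 − 64 = 14, 74 − 46 = 28.

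**4. How far the baseline gain can be trusted.** When only half of patients keep their prior rate (6% per year, 800 trials), the offset model goes from 79/64/49% to 80/67/52% on adding baseline, a gain of 1/3/3 points; across runs it was about 1–5.

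Another view uses SD × √(1 − r²) in the step 1 formula, where r is the unknown correlation with baseline. At SD 0.75, 65% becomes 70%, 78% or 91% for r = 0.3, 0.5 or 0.7. At SD 1, 42% becomes 46%, 53% or 70%.

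**5. Negative binomial version** (1,000 trials, 10% dropout spread over three years, stable rates, three-year look-back). At SD about 0.75: t-test 62%, offset 66%, offset and baseline 80%. At SD about 1.0: 39%, 45% and 74%. A one-year look-back gives 76% and 61% for the full model.

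**6. Type I error.** In these negative binomial runs the t-test gave 4.5–5.0% and the baseline-adjusted model 4.2–5.9%. Without baseline, the offset models reached 6.5–6.9% at the highest dispersion, where simulation error is √(0.05 × 0.95/1000) = 0.7 points.

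**7. Silent recurrence.** Imaging at Visits 2–9 is at the investigator's clinical judgement (section 10.2), whereas everyone who reaches Visit 10 has a research CT (sections 9.1.6 and 10.3). Detection of silent events is therefore not proportional to time, and a log-time offset does not correct for a scan that early leavers never have.

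**The case against.** The plan calls dropout small, asks people who stop treatment to keep attending, and takes the endpoint from routine records (section 5.1). Stopping treatment therefore need not end follow-up, and with complete follow-up the offset gains almost nothing. Heavy dropout of 15% per year is hard to call small. This stands, and it is why the gain must be given as a range starting near zero.

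The large baseline gain requires individual rates to be stable. The documents give no correlation, and users of thiol drugs are asked to stop 12 weeks before treatment (sections 4.1 and 7.1), so their earlier rate may reflect a different regimen. This also stands. The 74–82% figures at 6% dropout are an upper guide.

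The SAP promised in section 15 could still change the method. True, but no such change is in the documents, and a dated look-back count has to be planned at Visit 1.

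A reader might go further and infer that the t-test is invalid or inflates false positives. The simulated type I error does not support that. Nor does the equal-variance assumption matter: the plan does not specify the pooled form, and with 25 per arm a Welch test performed almost identically (70/59/40% against 71/59/41%). Finally, annualised per-person rates are inferred from the sample-size units, not stated. If raw three-year counts were meant, early leavers would look like low stone formers, so the definition is needed either way.

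**Conclusion.** The point holds as a loss of efficiency and a gap in specification. The rate is undefined, the test takes no account of length of follow-up, and recorded stone history goes unused. Type I error of the planned test is not in question.

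The sizes rest on 25 per arm, 1 versus 0.5 events per year and k between 0.25 and 1.0. The offset is worth about 0–2 points of power with no dropout, 4–8 at 6% per year and 9–15 at 15% per year. At 6% per year the baseline covariate adds between 1–5 points (half of patients keep their prior rate) and 4–28 points (all do).

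It would be tempting to conclude that the better model rescues the trial. It does not: even with fully stable rates, power stays below 90% in every simulated setting reported here. The change is worth making because it is cheap.

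**What to change.** - **Synopsis:** define the event count and time at risk. Replace the t-test with a negative binomial or overdispersed Poisson regression of event count on arm, with log(time at risk in the three-year period) as offset and the stone-event rate over a fixed pre-enrolment look-back (three years, for example) as covariate. Report the rate ratio with 95% CI and a rate difference alongside. Keep the t-test as a sensitivity analysis.
- **Section 15.2:** add the same model, since the section names no test. Note in section 15.3 that the sample size was based on a t-test.
- **Silent recurrence:** apply the offset model to symptomatic events and to silent events found during follow-up. Analyse silent recurrence first found on the month-36 CT separately.
- **Section 10.1:** record a dated count of stone events over the look-back, with rules for what counts.
- **Timing:** fix all of this before the unblinded interim analysis. State a small-sample reference distribution, or a re-randomisation test as a check, given the 6.5–6.9% seen for the unadjusted count models at high dispersion.

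Cost: protocol and SAP wording, and collection and checking of the look-back count; no extra patients or visits. The main estimate becomes a ratio, which is less direct than a difference.

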#### 3.2 Secondary Objectives

The secondary objectives of this study are to determine the effect of ALA on quantitative urinary cystine, cystine solubility, and metallomic and metabolomics profiles in participants with cystinuria. Quantitative urinary cystine is determined by 24-hour urine collection. The metallomic and metabolomics profiles of urine and stone samples will be compared in our lab as a new set of markers to understand how ALA has an effect on the stone-forming process and how its efficacy can be followed during treatment.

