## **15 STATISTICAL METHODS AND CONSIDERATIONS**

Prior to the analysis of the final study data, a detailed Statistical Analysis Plan (SAP) will be written describing all analyses that will be performed. The SAP will contain any modifications to the analysis plan described below.

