### **15.1 Data Sets Analyzed**

Data sets from all participants enrolled in the study will be analyzed.

The primary efficacy endpoint will be assessed by medical history and physical exam, in addition to radiographic imaging performed at each study visit.

The secondary efficacy endpoints will be assessed by 24-hour urine collections (Litholink, Chicago, IL), and the analysis of the metallomic and metabolomics profiles of urine and stone samples that are collected.

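### Metallomic and metabolomic profiles are compared by repeated-measures ANOVA with no control for the number of features, so marker claims made feature by feature would be unreliable

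*Combined protocol and SAP*

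**What the plan says.** The only analysis method for the profiles is in the synopsis, under Statistics / Primary Analysis Plan: the secondary analysis will "compare quantitative urinary cystine, and metallomic and metabolomics profiles using repeated measures of analysis of variance". Section 15 of the body covers data sets, the primary endpoint and sample size. The contents page lists a section on analysis of secondary endpoints, but the body has none.

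The profiles are broad. The synopsis lists "urinary, blood, and stone metallomic and metabolomic profiling" among the efficacy evaluations. Section 4.1 describes the platforms: "This is comprised of mass spectrometry and elemental analysis of samples performed in our research lab". No feature list or count is given.

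The profiles also have formal standing. Section 3.2 makes them a secondary objective and says they "will be compared in our lab as a new set of markers to understand how ALA has an effect on the stone-forming process". Section 15.1 names them, with the 24-hour urine collections, as the means of assessing the secondary efficacy endpoints. Nothing labels them exploratory.

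A two-sided 0.05 level appears only in the sample-size text for the primary endpoint. Section 15 promises a detailed SAP before the final analysis and adds that "The SAP will contain any modifications to the analysis plan described below". It does not mention multiplicity.

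**The concern.** Repeated-measures ANOVA handles one outcome at a time, whereas a profile is many outcomes. The natural way to apply the stated method is to run it once per feature, and then the number of false positives grows with the number of features. Because the profiles are meant to yield markers, the features that cross the threshold are the ones likely to be reported and followed up. Without an error-rate rule, a reader could not tell how many of them chance alone would have produced. With "target enrollment of 50 participants (25 for each treatment arm"), there is little room to confirm a candidate marker inside the same trial.

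**Working it through.** The documents give no feature count, familywise error or false-discovery rate for the profiles, so there is no figure of the plan's own to reproduce.

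**Inputs**
- Method: repeated-measures ANOVA (synopsis).
- Sample types: urine, blood and stone (synopsis). Profile types: metallomic and metabolomic. That makes up to 3 × 2 = 6 panels.
- Number of features, m: not stated, so a range is shown.
- Level: two-sided 0.05 per feature. This is assumed, because the documents state it only for the primary endpoint.
- Tests per feature: one. This is also assumed; a separate group-by-time test would add more.
- Correlation between features: not stated. Values of 0, 0.3, 0.6, 0.7 and 0.9 are shown.

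**Expected false markers when ALA has no effect.** This is 0.05 × m: 1 for 20 features, 5 for 100, 25 for 500. It holds at any correlation.

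**Chance of at least one, independent features.** The formula is 1 − 0.95^m.
- m = 6: 1 − 0.735 = 26%
- m = 13: 1 − 0.513 = 49%
- m = 14: 1 − 0.488 = 51%
- m = 50: 1 − 0.077 = 92%
- m = 100: 1 − 0.006 = 99%

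The 50% line lies at ln 0.5 / ln 0.95 = 13.5, so it is crossed at 14 features. Three features in each of six panels would give m = 18 and 1 − 0.95^18 = 60%.

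**Chance of at least one, correlated features.** Let the test statistics be standard normal with common correlation ρ, and let c = 1.96. Given a shared normal factor u, the chance that one feature stays below the threshold is q(u) = Φ((c − √ρ·u)/√(1 − ρ)) − Φ((−c − √ρ·u)/√(1 − ρ)). The chance of at least one false marker is 1 − E[q(u)^m], found by numerical integration.

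| ρ | m = 50 | m = 100 | m = 200 | m at which 50% is reached |
|---|---|---|---|---|
| 0 | 92% | 99% | >99.9% | 14 |
| 0.3 | 81% | 94% | 99% | 18 |
| 0.6 | 51% | 64% | 77% | 47 |
| 0.7 | 40% | 50% | 60% | 101 |
| 0.9 | 19% | 22% | 25% | not reached by 1000 (33%) |

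**Check of possible remedies.** When no feature is affected, Benjamini-Hochberg at 5% over one family holds the chance of any false marker to 5% for independent or positively dependent features. Run separately at 5% in six independent families, it leaves 1 − 0.95^6 = 26%. In four families (urine and blood, two platforms) it leaves 1 − 0.95^4 = 19%. Splitting 5% over four families gives 1.25% each, and 1 − 0.9875^4 = 4.9%.

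**The case against.** The strongest case on the other side is that much of the size of this problem is assumed. The plan does not say that features are tested one by one, does not set 0.05 for secondary endpoints, and gives neither a feature count nor a correlation. Section 3.2 sets no rule by which a significant feature becomes a marker. The trial calls itself a pilot, and a detailed SAP that could add a rule is still to be written. All of this stands, and it is why the probabilities are given as a range. It does not remove the gap: the synopsis sentence is the only stated method, and the promise of a SAP says nothing about multiplicity.

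Two stronger readings are tempting. A reader might infer that at least one false marker is more likely than not whatever the panel, and almost certain for a large one. The documents do not support that. With 6 independent features the chance is 26%, and at correlation 0.6 it is 64% for 100 features and 77% for 200.

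A reader might also infer that the mechanism objective cannot be answered. Section 4.1 rests mechanism on quantitative urinary cystine and cystine solubility as well as on the profiles. Section 2 names candidate pathways in advance, including zinc and glutathione, against which profile results can be read.

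**Conclusion.** The point holds as a conditional one. Secondary efficacy endpoints that consist of many features have a one-outcome-at-a-time method and no error-rate control. If each feature is tested once at two-sided 0.05, about 5 per 100 will appear as markers when ALA does nothing. The chance of at least one passes 50% from 14 independent features, 18 at correlation 0.3, 47 at 0.6 and 101 at 0.7. Marker claims would therefore be unreliable. The effect is confined to the profiles: the error rate of the primary endpoint is untouched, and urinary cystine is a single measure outside the problem. This should be corrected before the data are analysed, but it does not threaten the trial's main conclusion.

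**What to change.** In the synopsis and the SAP:

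1. Name one contrast per urine and blood feature: the difference between arms over the on-treatment visits.
2. Apply Benjamini-Hochberg at a 5% false-discovery rate across all urine and blood features on both platforms together. If it is run per platform and sample type instead, split the 5% across the families.
3. Call a feature a marker only if it passes, and label all others exploratory.
4. Report stone profiles descriptively. Stone samples exist only in participants who passed a stone or had one removed, which is itself part of the primary endpoint (Section 5.1), so an arm comparison would be made within groups selected by outcome.
5. Keep urinary cystine outside this family.
6. State whether blood belongs to the endpoint. The synopsis includes it, while Sections 3.2 and 15.1 name only urine and stone.

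The cost is SAP wording and a standard adjustment step. The statistical price is fewer declared features and some weak true signals lost. A conservative bound comes from Bonferroni over 100 features: with 25 per arm and a true difference of 1 SD, t-test power falls from 93% at 0.05 to 43% at 0.0005. Benjamini-Hochberg rejects everything Bonferroni rejects, so its loss is no greater than this.
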